### **Offspring**

*Through the course of the 10-year study, the incidence of birth defects/congenital malformations (total, and individual defects where appropriate national norms are, or will become, available), premature birth, low birth weight, and neonatal intensive care among women with MemoryGel implants will be estimated simply as the ratio of the number of offspring with these conditions to the total number of offspring of MemoryGel study participants. Ninety-five percent confidence intervals will be computed. The incidence of chronic illnesses (such as autoimmune disorders, cancer, and neurological disease), among children born to study participants after implantation of MemoryGel implants will be estimated as the ratio of number of new cases to the number of person-years. Ninety-five percent confidence intervals will be computed.*

*The relative risk for women with MemoryGel implants as compared to national norms will be estimated, standardizing for age, race, and other relevant characteristics of the mother, when appropriate. The relative risks will be tested for significance using one-sided tests conducted at the 0.05 level of significance. Ninety-five percent confidence intervals will be computed. The sources for the comparison data may include, as appropriate, relevant historical controls such as National Birth Defects Prevention Network, PRAMS, FASTER trial, the California Birth Defects Monitoring Registry, National Health and Nutrition Examination Survey (NHANES), and/or other reliable and relevant sources, including new sources that may become available during the course of this postapproval study, such as the National Children's Study.*

### **Complications/Reoperations**

*The cumulative incidence of key local complications (breast pain, infection, rupture, capsular contracture (Baker grades I-IV), explantation, and reoperation) for women with MemoryGel implants will be estimated based on the annual questionnaires as well as the three physician evaluations for the MemoryGel participants using Kaplan-Meier methodology to estimate the time to the first occurrence of the complication or reoperation. Ninety-five percent confidence intervals will be computed. In addition, the relative frequency of reasons for reoperation will be computed.*

### **Reproductive**

*Incidence of reproductive outcomes (miscarriage and stillbirth) will be estimated as the ratio of the number of women with these outcomes to the total number of pregnancies among MemoryGel participants. The relative risks will be tested for significance using one-sided tests conducted at the 0.05 level of significance. Ninety-five percent confidence intervals will be computed.*

*The relative risk of reproductive difficulties for women with MemoryGel implants compared to national norms will be estimated, standardizing for age, race, and other relevant characteristics of the mother, when appropriate. The sources for the comparison data may include, as appropriate, relevant historical controls as Burkman et al. (2003), Centers for Disease Control National Survey of Family Growth, Centers for Disease Control Vital and Health Statistics, National Birth Defects Prevention Network, FASTER trial, and/or other reliable and relevant sources, including new sources that may become available during the course of this study.*

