**Table 1. ORIGINAL POSTAPPROVAL STUDY OBJECTIVES**

Complication/ Condition/ Disease	Issues to be Addressed
Local Complications	
 
• What are the Kaplan-Meier (KM) complication rates over time, including removal and reoperation rates?
 
• What are the reasons for reoperation over time?
 

Connective Tissue Disease (CTD)	
 
• What are the types and rates of CTD diseases reported for women receiving Mentor MemoryGel implants and controls?
 

Rheumatological Signs and Symptoms	
 
• What are the types and rates of rheumatological signs and symptoms reported for women receiving Mentor MemoryGel implants and controls?
 

Neurological Disease	
 
• What are the types and rates of neurological diseases reported for women receiving Mentor MemoryGel implants and controls?
 

Neurological Signs and Symptoms	
 
• What are the types and rates of neurological signs and symptoms reported for women receiving Mentor MemoryGel implants and control group?
 

Offspring	
 
• What are the rates of birth defects/congenital malformations (such as cleft lip, cleft palate, neural tube defect, esophageal deformity, and pyloric stenosis), premature birth, low birth weight, neonatal intensive care, and chronic illnesses (such as autoimmune disorders, cancer, and neurological disease) in children born to women receiving Mentor MemoryGel implants and controls?
 

Reproductive	
 
• Of those women who attempted to have children, what are the rates of miscarriage and stillbirths for women receiving Mentor MemoryGel implants and controls?
 

Lactation	
 
• Of those women who attempted to breast feed, how many were able in each of the groups (women receiving Mentor MemoryGel implants and controls)? What are the types and rates of lactation problems for women receiving Mentor MemoryGel implants and controls?
 

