### 3.0 DESIGN

This protocol amendment includes participant follow-up only. Study enrollment has been closed since 15 Oct 2008 and no new study participants will be enrolled. Data collection will only take place if a participant requires a secondary procedure/reoperation. There are no longer requirements for scheduled office visits or annual participant questionnaires. The study is currently in year 7 and follow-up will continue through 10 years or until the National Breast Implant Registry opens for data collection, whichever occurs first.

As in the original protocol, there will be no concurrent controls needed as a source of comparison for secondary procedures/reoperations (see local complications category in original study design Tables 1 and 2). Thus, saline implant participants will not have data collected under this amended protocol.

Mentor will employ third party study entities that will be responsible for the following: (1) collecting data from surgeons; (2) entering data into and administering the study database; (3) generating follow-up reports as well as datasets; (4) meeting with Mentor on a regular basis; and (5) analyzing the study data. Mentor will be responsible for: (1) IRB approval; (2) monitoring third party entities; (3) analyzing the study data; and (4) periodic reporting to FDA.

The postapproval study was originally designed as follows:

*MemoryGel™ PAS uses a current cohort design of the first 41,900 women receiving Mentor's MemoryGel implants, with 10 years of follow-up. It will include augmentation, reconstruction, and revision patients, each in their naturally occurring proportions at participating study sites.*

*For the purpose of assessing rheumatological and neurological signs and symptoms, there also will be 1,000 saline breast implant patients from the participating surgeons' practices who will serve as concurrent controls. Concurrent control participants will be enrolled by approximately 30 physicians who routinely use saline implants. These investigative sites will be selected with the objective of obtaining the desired number of controls in an appropriate time frame, e.g. roughly the same time frame as the recruitment of MemoryGel subjects. These sites are to enroll all saline subjects meeting the specified eligibility criteria until 1,000 controls are recruited into this study.*

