#### Complications/Reoperations

The cumulative incidence of key local complications (explantation, and reoperation) for women with MemoryGel implants will be estimated based on physician evaluations for the MemoryGel participants using Kaplan-Meier methodology to estimate the time to the first occurrence of the complication or reoperation. Ninety-five percent confidence intervals will be computed. In addition, the relative frequency of reasons for reoperation will be computed.

Under the original protocol, the purpose of the inclusion of the saline participants was to serve as concurrent controls for assessing rheumatologic and neurologic signs. Rheumatological and neurological data will not be collected under this protocol amendment.

Mentor will generate the following final clinical study reports for submission to FDA:

- One final report at the end of the study phase conducted under Amendment 1, including data from beginning of the study through the end of the study phase under Amendment 1. The statistical analysis will be conducted as described in the original protocol (see below).
- One final report at the end of the study phase conducted under Amendment 2, including data from the execution of Amendment 2 to the end of the study. The statistical analysis will be conducted as described above.

The original analyses conducted to address each of the postapproval study's original objectives are identified below and correspond to issues outlined in Table 1:

*It is important to recognize that this study is observational. As a result, data from this study can be used only to establish association, not causality, and data should be evaluated within the context of the broader composite of literature relating to these issues. All of the analyses, except for the analyses of rheumatological and neurological signs and symptoms, will be based on the MemoryGel participants only.*

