**Lactation**

*The rate at which women with MemoryGel breast implants are able to breast feed will be examined. For each MemoryGel participant who gives birth during the 10-year study period, the proportion of births for which she is able to breast feed successfully among all births for which she desires to breast feed will be calculated. This proportion will be averaged across MemoryGel participants.*

*The relative risk of lactation difficulties for women with MemoryGel implants as compared to national norms or other similar women without these implants (e.g., other plastic surgery controls, if available) will be estimated, standardizing for age, race, and other relevant characteristics of the mother, when appropriate. The sources for the comparison data may include, as appropriate, relevant historical controls such as PRAMS, and/or other reliable and relevant sources, including new sources that may become available during the course of this postapproval study.*

*In addition, the relative frequencies of various types of lactation difficulties will be calculated.*

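### Miscarriage and stillbirth incidence divides affected women by pregnancies, so it cannot exceed, and usually understates, both the per-pregnancy rate and the rate per woman ever pregnant

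*Combined protocol and SAP*

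**What the plan says.** The Reproductive paragraph of Section 11.1 defines incidence as "the ratio of the number of women with these outcomes to the total number of pregnancies among MemoryGel participants". On inference it says: "The relative risks will be tested for significance using one-sided tests conducted at the 0.05 level of significance". The comparator is national norms, standardised for age, race and other maternal characteristics where appropriate. Several possible sources are named, but not the unit in which their rates are expressed.

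Table 1 in Section 2.0 puts the question on a third base: "Of those women who attempted to have children, what are the rates of miscarriage and stillbirths".

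The neighbouring analyses keep one unit above and below the line. Offspring outcomes use "the ratio of the number of offspring with these conditions to the total number of offspring of MemoryGel study participants". Lactation uses, for each woman, "the proportion of births for which she is able to breast feed successfully among all births for which she desires to breast feed", averaged over women.

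Amendment 2 collects no reproductive data, but this text still applies. Section 11.1 (Complications/Reoperations) requires a final report for the Amendment 1 phase, "including data from beginning of the study through the end of the study phase under Amendment 1", analysed by the original methods reproduced in that section.

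**The concern.** A ratio of women to pregnancies is neither a risk per pregnancy nor a risk per woman. Repeat losses in one woman enlarge the denominator only, and successful pregnancies in a woman already counted as affected dilute her contribution. A published norm will normally be in one unit or the other, so the relative risk compares unlike quantities. Standardising for age and race adjusts the case mix and leaves the unit mismatch in place.

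Against a norm per pregnancy or per woman ever pregnant, the relative risk is pulled downward. If the one-sided test looks for excess risk, that works against finding one. The Reproductive paragraph does not state the direction; the inference comes from Section 11.2, where the one-sided sample-size test is framed as detecting a relative risk of 2.0.

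**Working it through.** The plan gives no figure for this analysis to reproduce. The direction can be proved; the size needs assumed inputs.

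**Direction.** Let W = women with at least one loss, L = pregnancies ending in loss, P = all pregnancies, N = women ever pregnant. The plan's estimator is W/P.

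- Each affected woman has at least one loss, so W ≤ L and W/P ≤ L/P. Equality holds only if no woman has a repeat loss.
- Each woman ever pregnant has at least one pregnancy, so N ≤ P and W/P ≤ W/N. With W > 0, equality holds only if every such woman has exactly one pregnancy.

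Enumerating all sets of 1 to 5 women with 0 to 3 pregnancies each gave 2,997 configurations with at least one pregnancy and no violation of either inequality.

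An illustration with assumed counts W = 130, L = 150, P = 1,000, N = 700: the plan gives 13.0%, the per-pregnancy rate is 15.0%, and the rate per woman ever pregnant is 130/700 = 18.6%. Against a per-pregnancy norm of 15% the plan reports a relative risk of 0.13/0.15 = 0.87 where the matched figure is 1.00.

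**Size against a per-pregnancy norm.** Assume shares w_k of women with k = 1, 2, 3 pregnancies and loss risk p per pregnancy. Then

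W/P = Σ w_k[1 − P0(k)] / Σ k·w_k,

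with P0(k) = (1 − p)^k for independent losses. For within-woman correlation ρ, P0(k) is beta-binomial: the product over i = 0 to k − 1 of (b + i)/(a + b + i), where a = p(1/ρ − 1) and b = (1 − p)(1/ρ − 1).

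For the 90/9/1% mix at p = 0.15, independent: (0.90×0.15 + 0.09×0.2775 + 0.01×0.3859)/1.11 = 0.1638/1.11 = 0.1476, which is 1.6% below 0.15.

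| Women with 1/2/3 pregnancies | Mean | W/P at p = 0.15 | Too low by | p = 0.10–0.20 | p = 0.15, ρ = 0.1–0.3 | True RR 1.20 reported as |
|---|---|---|---|---|---|---|
| 90/9/1% | 1.11 | 0.1476 | 1.6% | 1.1–2.1% | 2.5–4.2% | 1.18 |
| 80/15/5% | 1.25 | 0.1447 | 3.5% | 2.4–4.6% | 5.4–8.8% | 1.15 |
| 50/35/15% | 1.65 | 0.1394 | 7.1% | 4.8–9.3% | 10.7–17.6% | 1.10 |

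The last column uses p = 0.18 against a norm of 0.15 with independent losses. For stillbirth at an assumed 0.5–1%, the ratio is 0.05–0.5% too low if independent and 0.6–5.1% with ρ = 0.05–0.1.

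The mixes with few repeats are the more plausible. The study is in year 7 (Section 3.0), follow-up through six years is 21.8% (Section 1.0), and women were discontinued after three years with neither a questionnaire nor a surgeon's form (Section 14.0).

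**Size against other norms.** Per woman ever pregnant, W/P = (W/N)/mean, for both outcomes. Per woman who attempted, with share c conceiving and assuming only those women conceive, W/P divided by the norm is 1/(c × mean).

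| Mean | Too low per woman ever pregnant | True RR 1.20 reported as | Ratio to per-attempter rate, c = 70% to 95% | Break-even c |
|---|---|---|---|---|
| 1.11 | 10% | 1.08 | 1.29 to 0.95 | 90% |
| 1.25 | 20% | 0.96 | 1.14 to 0.84 | 80% |
| 1.65 | 39% | 0.73 | 0.87 to 0.64 | 61% |

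On the Table 1 base the ratio can therefore err in either direction.

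**The case against.** The strongest reply is that the effect is small and the wording may be a slip. With few repeat pregnancies, independent losses and a per-pregnancy norm, which is the natural partner for a denominator of pregnancies, miscarriage is 1.6% to 3.5% too low and stillbirth at most 0.24%. The large figures need a norm in a unit the plan never names. The authors may have written women where they meant pregnancies. The questionnaire is not in these documents, so how losses were recorded is unknown. Selection at 21.8% follow-up may well be the larger error.

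Much of this stands, and it limits the weight of the point. It does not rescue the definition. The text says women, nothing elsewhere corrects it, and an analyst following it exactly gets the mismatched ratio. Because the norm's unit is left open, the larger errors are not excluded.

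The per-pregnancy figures are also not bounds, because they treat the number of pregnancies as unrelated to earlier outcomes. At a mean of 1.11 and 15% risk, if every repeat pregnancy follows a first loss, the ratio is 0.15/1.11 = 0.135, or 9.9% too low instead of 1.6%. If women stopped after a loss, no one would have two and the shortfall would be zero.

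**Conclusion.** The concern holds. That the estimator is at or below both matched rates is certain from the definition. How far below cannot be determined from the documents. Under the assumed mixes with independent losses, miscarriage is understated by roughly 2% to 7% against a per-pregnancy norm, and more if losses cluster within women. Both outcomes are understated by 10% to 39% against a norm per woman ever pregnant. Against a norm per woman who attempted, the direction is undetermined.

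This is one secondary outcome in one report and does not threaten the study's main results. It should still be corrected, because the error is built into the definition and, unlike the selection problem, can be removed.

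**What to change.** For the Amendment 1 final report, replace the definition in the Reproductive paragraph with wording such as:

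> Miscarriage incidence and, separately, stillbirth incidence will be the number of pregnancies ending in that outcome divided by all pregnancies reported by MemoryGel participants. Confidence intervals and tests will allow for pregnancies clustered within woman. Comparison will be made only with norms expressed per pregnancy. If outcomes were not recorded for each pregnancy, incidence will be affected women divided by women with at least one pregnancy, compared only with a norm in that unit over a comparable period.

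Reconcile the chosen unit with the Table 1 base of women who attempted to have children. Record the change as made after data collection, and show the ratio now in the plan alongside, so that any annual report that used it remains comparable.

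The cost is a few sentences and one extra row per outcome, with no new data collection. The clustered interval is wider by the factor √(1 + ρ(Σk²w_k/Σk·w_k − 1)): about 1–3%, 2–7% and 5–14% for the three mixes at ρ = 0.1–0.3. Norms in the other unit can no longer be used. Annual questionnaires have ended, so missing per-pregnancy detail cannot be collected now. The fallback covers that case, but if no suitable per-woman norm exists, the rate would have to be reported without a comparison.

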**Lactation**

*The rate at which women with MemoryGel breast implants are able to breast feed will be examined. For each MemoryGel participant who gives birth during the 10-year study period, the proportion of births for which she is able to breast feed successfully among all births for which she desires to breast feed will be calculated. This proportion will be averaged across MemoryGel participants.*

*The relative risk of lactation difficulties for women with MemoryGel implants as compared to national norms or other similar women without these implants (e.g., other plastic surgery controls, if available) will be estimated, standardizing for age, race, and other relevant characteristics of the mother, when appropriate. The sources for the comparison data may include, as appropriate, relevant historical controls such as PRAMS, and/or other reliable and relevant sources, including new sources that may become available during the course of this postapproval study.*

*In addition, the relative frequencies of various types of lactation difficulties will be calculated.*

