### **Eligibility Criteria: MemoryGel Breast Implant Participants**

#### **Inclusion Criteria**

To be included in the study, each MemoryGel participant must be a woman who:

1. Is a candidate for breast augmentation with Mentor MemoryGel breast implants and is at least 22 years old (primary or revision) **OR** is a candidate for breast reconstruction (primary or revision) with Mentor MemoryGel breast implants
2. Signs an Acknowledgement of Informed Decision from the patient brochure
3. Signs an Informed Consent Form and an Authorization to Disclose Health Information and Release Medical Records
4. Completes the baseline questionnaire (as evidenced by the participant's signature on the last page of the questionnaire).
5. Agrees to authorize return of the device(s) to Mentor if the device is explanted
6. Agrees via Informed Consent to comply with study follow-up, including full participation in all follow-up questionnaires and responding to questionnaires in their entirety
7. Is a U.S. resident

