### **Eligibility Criteria: Saline Breast Implant Control Participants**

#### **Inclusion Criteria**

To be included in the study, each saline control participant must be a woman who:

1. Is a candidate for breast augmentation and is at least 18 years old (primary or revision) **OR** is a candidate for breast reconstruction (primary or revision) with saline breast implants.
2. Signs an Informed Consent Form and an Authorization to Disclose Health Information and Release Medical Records
3. Completes the baseline questionnaire (as evidenced by the participant's signature on the last page of the questionnaire).
4. Agrees to authorize return of the device(s) to Mentor if they are Mentor devices.
5. Agrees via Informed Consent to comply with study follow-up, including full participation in all follow-up questionnaires and responding to questionnaires in their entirety
6. Is a U.S. resident

---

 Breast augmentation includes primary breast augmentation to increase the breast size, as well as revision surgery to correct or improve the result of an original primary breast augmentation surgery.

 Breast reconstruction includes primary reconstruction to replace breast tissue that has been removed due to cancer or trauma or that has failed to develop properly due to a severe breast abnormality. Breast reconstruction includes revision surgery to correct or improve the result of an original primary breast reconstruction surgery.

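### The lactation relative risk pools reconstruction with augmentation women, so earlier loss or absence of breast tissue is mixed into the association reported for the implants

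*Combined protocol and SAP*

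**What the plan says.** **Population and rate.** Section 11.1, Lactation, begins "For each MemoryGel participant who gives birth during the 10-year study period". For each such woman it takes the proportion of births with successful breast feeding "among all births for which she desires to breast feed will be calculated", then averages these proportions over all MemoryGel participants.

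**Comparison.** The same section plans "The relative risk of lactation difficulties for women with MemoryGel implants as compared to national norms". The sentence continues: it also allows similar women without the implants, for example other plastic surgery patients, if they can be had. Standardisation is to cover age, race and further unnamed maternal characteristics where appropriate. Table 2 (Section 3.0) lists only national norms as the lactation control. PRAMS is the one source named, in the table's footnote and in Section 11.1, and both leave room for other sources.

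**Who is in the cohort.** Section 3.0 says: "It will include augmentation, reconstruction, and revision patients, each in their naturally occurring proportions at participating study sites". Footnote 2 in Section 4.0 says: "Breast reconstruction includes primary reconstruction to replace breast tissue that has been removed due to cancer or trauma or that has failed to develop properly".

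**Objective.** Table 1 (Section 2.0) asks: "Of those women who attempted to breast feed, how many were able in each of the groups". It sets no limit by indication.

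**Status.** Amendment 2 collects no lactation data. Section 11.1 nevertheless requires a final report on the Amendment 1 phase, analysed as the original protocol describes, so the lactation text still governs that report.

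**The concern.** The protocol's own definition places in the lactation analysis women who had reduced or absent breast tissue before they received a study implant. Some may wish to breast feed and be unable to for that reason alone. National norms describe mothers in general.

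The ratio would then combine two things: any association between the implant and lactation, and the consequence of the condition that led to reconstruction. The second pushes the ratio upward, and a larger cohort does not remove it. A reader of the Amendment 1 final report who saw a raised relative risk could not tell how much came from each.

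**Working it through.** **Plan's own figure.** None exists to reproduce. The documents give no expected rate, margin, power or sample size for lactation.

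**Text check.** Four places need to be read together.

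1. Section 11.1 takes in every participant who gives birth; indication is not mentioned.
2. Section 3.0 and inclusion criterion 1 (Section 4.0) admit both augmentation and reconstruction, primary or revision.
3. Footnote 2 in Section 4.0 defines reconstruction by missing or undeveloped tissue.
4. Table 2 supplies norms as the control.

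No step removes, separates or adjusts for indication by name.

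**Illustration with no implant association.** Let

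- s = share of reconstruction women among those who contribute a proportion (women with at least one birth for which they wished to breast feed);
- q0 = difficulty rate with intact tissue, taken as equal to the norm;
- qr = difficulty rate among reconstruction women.

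All three are assumptions; the documents give none of them. Difficulty is taken as one minus the success proportion, and women are weighted equally because the plan averages over participants.

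Apparent RR = [(1 − s)·q0 + s·qr] / q0 = 1 + s·(qr − q0)/q0.

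This exceeds 1 whenever s > 0 and qr > q0. Two worked cases:

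- s = 5%, q0 = 20%, qr = 100%: 1 + 0.05 × 0.80/0.20 = 1.20.
- s = 5%, q0 = 20%, qr = 50% (as with many one-sided cases): 1 + 0.05 × 0.30/0.20 = 1.075.

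| q0 | s | RR at qr = 50% | RR at qr = 100% |
|---|---|---|---|
| 10% | 1% | 1.04 | 1.09 |
| 10% | 5% | 1.20 | 1.45 |
| 20% | 1% | 1.015 | 1.04 |
| 20% | 5% | 1.075 | 1.20 |
| 30% | 1% | 1.007 | 1.023 |
| 30% | 5% | 1.033 | 1.117 |

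For shares of 1% to 5% the range is 1.01 to 1.45. The excess over 1 is proportional to s. With reconstruction women left out of the comparison, s = 0 and the ratio is 1.00 by construction.

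**The case against.** Several points on the other side have force.

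- **Comparator.** A reader might infer that national norms are the only comparator. Section 11.1 does not say so; it permits similar women without the implants. That stands as a correction. But the alternative depends on availability, Table 2 does not list it, and other plastic surgery patients need not share the same tissue loss.
- **Standardisation.** A reader might infer that adjustment could never deal with the problem. The text leaves room for breast surgery history among the unnamed maternal characteristics. What can fairly be said is that the factor is not named, its use is optional, and it works only if the comparison source records it.
- **Denominator.** Women who do not wish to breast feed because of their surgery drop out. Table 1 refers to women who attempted it, which would keep fewer women who cannot. Both wordings reduce s, but neither is sure to bring it to zero: women who wish to, or try, and cannot still remain. The two wordings differ and should be reconciled in any case.
- **Not all reconstruction women are unable.** One-sided surgery or partly developed tissue may leave function. This lowers qr; the documents give no laterality.
- **Consequences.** Section 11.1 limits the study to association rather than cause. Unlike the disease, offspring and reproductive analyses, the lactation analysis specifies no significance test, so no formal decision rests on the ratio. This lowers the stakes but does not correct the figure that would be reported.
- **Objective.** Table 1 covers all women who receive the implants, so removing reconstruction women from the breast-feeding rate itself would change the stated objective. This stands, and it limits the fix to the comparison with norms.

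**Conclusion.** The point holds as a problem of comparability. As written, the relative risk against norms mixes prior loss or absence of breast tissue into the association reported for the implants. Its direction is upward, provided that some reconstruction women are in the denominator and that they have more difficulty than mothers in general. The second condition is reasoning from the protocol's definition of reconstruction, not a figure in it.

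The size cannot be established from the documents. Under the assumed inputs (norm difficulty rate 10% to 30%, reconstruction difficulty rate 50% to 100%, share 1% to 5%) the apparent ratio is about 1.01 to 1.45 with no implant association. It lies near the bottom of that range if few reconstruction women gave birth and wished to breast feed.

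A reader might go further and infer that the plan attributes anatomical inability to the implant, or that a material false signal is certain. The documents support neither: they disclaim causality and give nothing from which to judge the size. Only the Amendment 1 final report is affected.

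**What to change.** In the Amendment 1 final report:

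1. Keep the planned breast-feeding rate for all participants as a descriptive figure, since Table 1 asks for it.
2. Report the same rate separately for augmentation (primary and revision) and reconstruction.
3. Restrict the relative risk against national norms to augmentation participants, unless a comparator with similar breast surgery history is available.

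Inclusion criterion 1 already separates the two indications, so the split should need no new data; the enrolment and operative forms are not among the documents, so confirm that indication is held in the database. The cost is one population rule for one comparison and slightly fewer births in it. The restriction removes this one source of bias; it does not otherwise make augmentation women comparable with mothers in general.
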